14.3.8.2 First supplementary estimand

The first supplementary estimand will use a combination of the *treatment policy and hypothetical strategies*, to handle the occurrence of non-pandemic and pandemic related intercurrent events, respectively. The treatment policy strategy attempts to quantify the effect of the decision to treat subjects with the randomized treatment and therefore ignores the occurrence of non-pandemic related intercurrent events.

This supplementary estimand will evaluate the treatment difference in the change in EASI score from baseline to Week 16 in the hypothetical scenario in which the COVID-19 pandemic did not occur and regardless of the occurrence of non-pandemic related intercurrent events. Under this hypothetical scenario, the potential outcomes for subjects experiencing a pandemic related intercurrent event are assumed to follow the observed outcome distribution, irrespective of the occurrence of non-pandemic related intercurrent events, among subjects in the same treatment group.

Main analysis

Data collected after the occurrence of a non-pandemic related intercurrent event will be included in the analysis. Whereas data collected after a pandemic related intercurrent event will be excluded from the analysis and 'treated as missing'.

Intermittent missing data will be imputed based on a Markov Chain Monte Carlo method, in order to obtain 1,000 copies of the data set with a monotone missing data pattern. Missing data, including data 'treated as missing' after the occurrence of a pandemic related intercurrent event, will be imputed assuming the data is MAR within each treatment group. For a given treatment group, the imputation model will be based on all data observed prior to the occurrence of pandemic related intercurrent events. In particular, data observed after the occurrence of non-pandemic related intercurrent events will be included in the imputation model, in line with the specified treatment policy approach for handling non-pandemic related intercurrent events.

For each of the 1,000 complete datasets, the change in EASI score from baseline to Week 16 will be analyzed using an ANCOVA model including treatment, and region (Japan, non-Japanese countries) as factors, and baseline EASI score as a covariate. The pooled estimates of the difference in the LS-mean change from baseline to Week 16, based on the observed margins, along with the associated 95% CIs and nominal p-values will be presented. Pooled inference will be based on applying Rubin's rules to the estimates and standard errors from the ANCOVA analysis of the imputed datasets.

Sensitivity analysis

A tipping point analysis will be performed based on implementing a delta-adjusted multiple imputation approach. The delta-adjusted imputation approach allows for missing data to be imputed under the MNAR assumption. Heuristically, the imputation strategy, adjusts/shifts the parameters of the MAR distribution based on the value of a numeric offset term, denoted by delta. The tipping point analysis will adjust the values of the parameters in the MAR distribution representing the mean change in EASI score from baseline to Weeks 1-16. The analysis will assess how robust the results of the main analysis are to varying departures from the MAR assumption within each active treatment group.

14.3.8.3 Second supplementary estimand

A second supplementary estimand will use a combination of the *composite* and *hypothetical strategies* to handle the occurrence of non-pandemic and pandemic related intercurrent events, respectively. In the context of this trial, the composite strategy attempts to quantify the effect of treatment, assuming that the occurrence of a non-pandemic related intercurrent event is indicative of subsequent treatment failure. For the primary endpoint, treatment failure will be defined as failing to obtain a decrease in EASI of at least 50% from baseline to Week 16.

This supplementary estimand evaluates the treatment difference in the change in EASI score from baseline to Week 16 in the hypothetical scenario in which the COVID-19 pandemic did not occur and assuming that the occurrence of non-pandemic related intercurrent events is indicative of subsequent treatment failure.

Main analysis

Data observed after the occurrence of an intercurrent event will be excluded from the analysis and "treated as missing". Intermittent missing data will be imputed using a Markov Chain Monte Carlo method, in order to obtain 1,000 copies of the data set with a monotone missing data pattern.

Monotone missing data that is not due to the pandemic and data "treated as missing" due to the occurrence of a non-pandemic related intercurrent event will be imputed under the MAR assumption, with the additional stipulation that the imputation model will be truncated in order to align with the assumption that

$$Y_{EASI,Week\ 16} > \frac{Y_{EASI,Baseline}}{2}.$$

The additional stipulation ensures that these subjects will be considered as non-responders based on the imputed Week 16 EASI score.

For subjects experiencing a pandemic related intercurrent event or with monotone missing data due to the pandemic, the imputation model needs to account for the possibility of experiencing a subsequent non-pandemic related intercurrent under the envisioned hypothetical scenario. Missing data will therefore be imputed from the joint distribution describing the time to experiencing a non-pandemic related intercurrent event and the longitudinal EASI score assessments under a MAR assumption. If the imputed time to first non-pandemic related intercurrent event is less than 16 weeks, all subsequent EASI scores for that subject will be imputed based on the above imputation model for non-pandemic related intercurrent events.

For each of the 1,000 complete datasets, the change in EASI score from baseline to Week 16 will be analyzed using an ANCOVA model including treatment and region (Japan, non-Japanese countries) as factors, and baseline EASI score as a covariate. The pooled estimates of the difference in the LS-mean change in EASI score from baseline to Week 16, based on the observed margins, along with the associated 95% CIs and nominal p-values will be presented. Pooled inference will be based on applying Rubin's rules to the estimates and standard errors from the ANCOVA analysis of the imputed datasets.

Panel 19 presents an overview of how observed and missing data will be handled according to the intercurrent events for the analyses of estimands.

Panel 19: Handling of intercurrent events and analyses of estimands for the primary endpoint

Events	Data observed or missing	Estimand strategy		
		Primary estimand	First supplementary estimand	Second supplementary estimand
Initiation of rescue treatment ^a	Observed	Treated as missing/Not used	Used	Treated as missing, MI (MAR ensuring NR)
	Missing	Not used	MI (MAR)	MI (MAR ensuring NR)
Permanent discontinuation of IMP independently of the COVID-19 pandemic	Observed	Treated as missing/Not used	Used	Treated as missing, MI (MAR ensuring NR)
	Missing	Not used	MI (MAR)	MI (MAR ensuring NR)
Permanent discontinuation of IMP due to the COVID-19 pandemic	Observed	Treated as missing/Not used	Treated as missing, MI (MAR)	Treated as missing, MI (JM/MAR ensuring NR)
	Missing	Not used	MI (MAR)	MI (JM/MAR ensuring NR)
No intercurrent events	Observed	Used	Used	Used
	Missing independently of the COVID-19 pandemic	Not used	MI (MAR)	MI (MAR ensuring NR)
	Missing due to the COVID-19 pandemic	Not used	MI (MAR)	MI (JM/MAR ensuring NR)

Abbreviations: COVID-19 = coronavirus disease 2019; IMP = investigational medicinal product; JM = joint model; MAR = missing at random; MI = multiple imputation; NR = non-response.

^a Initiation of rescue treatment is considered an intercurrent event regardless of the relatedness to the COVID-19 pandemic.

THIS DOCUMENT CONTAINS CONFIDENTIAL INFORMATION AND MUST NOT BE COPIED OR MADE AVAILABLE TO ANY THIRD PARTY WITHOUT THE PRIOR WRITTEN CONSENT OF THE LEO PHARMA GROUP

14.3.8.4 Exposure-response modeling of LEO 152020

To explore the exposure-response relationship of LEO 152020, the change in EASI score from baseline to Week 16 will be assessed based on an ANCOVA model, including the C_{trough} values at Week 16 and the baseline EASI score as covariates and region (Japan, non-Japanese countries) as a factor. Data observed after the occurrence of an intercurrent event, will be excluded from the analysis and "treated as missing". Week 16 data, that is either missing or "treated as missing" due to the occurrence of an intercurrent event, will be assumed to be missing at random. The difference in the LS-mean change in EASI score from baseline to Week 16, based on the observed margins, along with the associated 95% CIs and nominal p-values will be presented. In case a linear relationship between change in EASI from baseline to Week 16 and C_{trough} cannot be shown, alternative models such as non-sigmoidal (with a hill coefficient =1) E_{max} or sigmoidal E_{max} will be considered. Further details regarding the goodness of fit criteria and the non-linear model will be described in the SAP.

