Statistical methods	
Primary and secondary endpoints:
 
A primary and 2 supplementary estimands will be defined for the primary endpoint, change in EASI from baseline to Week 16, in order to assess different clinical questions of interest.
 
 • The primary estimand for the primary endpoint will use the hypothetical strategy to handle the occurrence of pre-defined intercurrent events (initiation of rescue treatment and permanent discontinuation of IMP). • A first supplementary estimand will use the treatment policy and hypothetical strategies to account for the occurrence of intercurrent events. • A second supplementary estimand will use the composite and hypothetical strategies to handle the occurrence of intercurrent events. 
For the main analysis of the primary estimand, data observed after the occurrence of an intercurrent event will be excluded from the analysis. Missing data will be assumed to be MAR. The primary endpoint will be analyzed using an MMRM including treatment, visit, visit by treatment interaction terms, and region (Japan, non-Japanese countries) as factors, and adjusting for the baseline EASI score as a covariate. The covariance matrix will be assumed to have an unstructured form and the Kenward-Rodger approximation will be used to estimate the denominator degrees of freedom.
 
To explore the exposure-response relationship, the change in EASI score from baseline to Week 16 will be assessed based on an ANCOVA model including region as a factor and C_{trough} at Week 16 and baseline EASI score as covariates. Data observed after the occurrence of an intercurrent event will be excluded and missing data will be assumed to be MAR.

	The secondary endpoint, number of AEs from baseline to Week 16+3 days per subject, will be reported descriptively by treatment group.
Signatory investigator	PPD [REDACTED], MD PPD [REDACTED] [REDACTED] Hannover, Germany
Sponsor	LEO Pharma A/S, [name]

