9.5 Rescue treatment

If medically necessary (i.e. to control intolerable worsening of AD symptoms), rescue treatment of AD may be provided to the subject at the discretion of the investigator. If possible, the investigator should attempt to limit the first step of rescue treatment to topical treatment and escalate to systemic treatment if the subject does not respond adequately to topical rescue treatment.

Topical rescue treatment

In this trial, topical rescue treatment of AD consists of TCS and TCI. Subjects provided with topical rescue treatment between first dose of IMP and Week 16 may continue treatment with the IMP and remain in the trial with no change to the visit schedule nor trial assessments/procedures.

Systemic rescue treatment.

If the subject is provided with systemic rescue treatment of AD at any time during the treatment period, treatment with IMP will immediately and permanently be discontinued (see also Section 9.7 for prohibited medications).

Before administering topical or systemic rescue treatment, the investigator may conduct efficacy and safety assessments (e.g. disease severity scores [EASI, vIGA-AD, and SCORAD], AEs, safety laboratory samples, PK blood sample, and concomitant medications/concurrent procedures). However, to safeguard subject safety and well-being, the assessments should only be conducted if the subject's health permits. To further attend to subject safety and well-being, an unscheduled visit, scheduled earlier than the next planned visit, may be arranged to administer the topical or systemic rescue treatment.

If the subject is permanently discontinued from IMP due to use of systemic rescue medication, every effort must be done to monitor the subject as described in Section 10.3.

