14.3.8.1 Primary estimand

The primary estimand will use the *hypothetical strategy* to handle the occurrence of intercurrent events. The estimand attempts to quantify the effect of treatment, in the hypothetical scenario, where subjects do not permanently discontinue IMP for any reason and where rescue medication is not made available prior to Week 16.

For subjects observed to experience an intercurrent event, the potential outcomes under the envisioned hypothetical scenario, are assumed to follow the outcome distribution for subjects in the same treatment group, who did not experience an intercurrent event.

The primary estimand assesses the expected benefit of the treatment when adhering to the treatment regimen in the context of the specified hypothetical scenario.

Main analysis

Data collected after permanent discontinuation of IMP, regardless of reason, or the initiation of rescue treatment will be excluded from the analysis and "treated as missing".

The endpoint will be analyzed using a MMRM. The model will include treatment, visit, visit by treatment interactions, and region (Japan, non-Japanese countries) as factors and be adjusted for the baseline EASI score as a covariate. The covariance matrix will be assumed to have an unstructured form and the Kenward-Roger approximation will be used to estimate the denominator degrees of freedom. Missing data, including data excluded due to the occurrence of an intercurrent event, is assumed to be MAR. The estimated LS-mean treatment differences, based on the observed margins, will be presented with 95% CIs and nominal p-values at each visit. The primary comparison is the treatment difference at Week 16, between the CCI and placebo groups.

Sensitivity analysis

The following sensitivity analyses will assess the robustness of the results of the main analysis with respect to the underlying statistical assumptions. The impact of the missing data assumptions on data excluded after the occurrence of an intercurrent event/due to the pandemic will not be considered in the sensitivity analyses, as the MAR assumption is aligned with the envisioned hypothetical scenario.

- Sensitivity analysis 1: Exclusion of subjects with monotone missing data at Week 1

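### The exposure-response ANCOVA uses no pre-event EASI, so its slope is modestly biased if intercurrent events follow poor interim response

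*Combined protocol and SAP*

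**What the plan says.** Section 14.3.8.4 specifies a single-timepoint ANCOVA with Week 16 C_trough and baseline EASI as covariates and region as a factor. Data after an intercurrent event are removed, and Week 16 values missing for any reason, including removal "due to the occurrence of an intercurrent event, will be assumed to be missing at random". The synopsis gives the same rule: "Data observed after the occurrence of an intercurrent event will be excluded and missing data will be assumed to be MAR". Neither place names an imputation step, a repeated-measures likelihood or an interim EASI term. What 14.3.8.4 leaves for later is limited: "Further details regarding the goodness of fit criteria and the non-linear model will be described in the SAP".

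For the same endpoint the plan does use pre-event EASI elsewhere. The primary estimand (14.3.8.1) is analysed with an MMRM over all visits. In the first supplementary estimand (14.3.8.2), missing data "will be imputed assuming the data is MAR within each treatment group", and only then: "For each of the 1,000 complete datasets, the change in EASI score from baseline to Week 16 will be analyzed using an ANCOVA model". The second supplementary estimand (14.3.8.3) also imputes before its ANCOVA. Panel 19 covers these three estimands and not the exposure-response model.

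**The concern.** MAR is an assumption, not a procedure. It protects an analysis only with respect to what that analysis conditions on, which here is trough, baseline EASI and region. EASI is scheduled at eight interim visits (Weeks 1 to 14), and none of those values enters the model.

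The protocol itself links events to poor response. Section 9.5 states: "If medically necessary (i.e. to control intolerable worsening of AD symptoms), rescue treatment of AD may be provided to the subject". Section 10.2 lists lack of efficacy among the reasons for stopping IMP, and 14.3.8.3 treats non-pandemic events as a sign of treatment failure. If subjects doing badly at Week 8 or 12 are more likely to drop out of the Week 16 data, the remaining subjects are a selected group, and the selection can vary with exposure.

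Exposure-response is the first-named part of the primary objective (section 6), and the trial is meant to identify efficacious doses and inform phase 3 dose selection (5.3, 12.1). A distorted slope misstates how response changes with exposure.

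**Working it through.** **The plan's own figures.** The plan gives no figure for the slope or its bias, so there is none to reproduce. The nearest are the Panel 17 powers. Calibrating a 64 versus 64 comparison at two-sided 5% to the stated 90.8% gives a standardised effect of 0.581, or 0.581 × 4.35 = 2.53 EASI points. At 48 versus 64 this gives 86.1% (stated 85.3%), and 79.3% after gatekeeping and Hochberg (stated 79.4%). Panel 17 is internally consistent, and none of it uses the exposure-response model.

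**When the ANCOVA is valid.** Write Y16 = a + bC + cB + region + e, where C is trough, B is baseline EASI and b < 0 means more improvement at higher exposure. Among event-free subjects, E(e | C, B, region) = −λ(C), the extent to which those who remain did better than expected.
- If missingness depends only on C, B and region, λ = 0 and b is unbiased.
- If events follow poor interim EASI, λ > 0 and the fitted slope is roughly b − dλ/dC.
- If low-exposure subjects respond worse and so have more events, λ falls with C and the slope moves toward zero.
- If poor responders leave mainly at high exposure, λ rises with C and the slope moves away from zero.
- If λ does not vary with C, the slope is unbiased.

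**Why the effect is modest.** With the AR(1) value of 0.65 from section 14.1, the Week 16 residual correlates 0.65 with Week 14, 0.65² = 0.42 with Week 12 and 0.65⁴ = 0.18 with Week 8 (two-weekly visits). Selection on an early value carries only weakly to Week 16.

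**Simulation inputs.**
- From the documents: residual variance 18.9 (SD √18.9 = 4.35), AR(1) 0.65, allocation 4:3:3:4 (64/48/48/64), Japan 28/224 = 12.5%, severity strata 30%/70%.
- Assumed, because redacted or not given: relative exposure 0/0.5/1/2 with placebo at zero, between-subject CV 50%, slope 0.35 residual SD per exposure unit at Week 16, and overall event rates of 10% to 40%.
- Event hazard: logit slope 1 (weak) or 2 (strong) per SD of last observed EASI change.

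The result is the estimated slope divided by the slope the same Week 16 ANCOVA would give with no events.

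| Assumed event rate | 10% | 15% | 25% | 40% |
|---|---|---|---|---|
| As planned, weak | 0.99 | 0.98 | 0.97 | 0.96 |
| As planned, strong | 0.97 | 0.95 | 0.94 | 0.91 |

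With imputation from pre-event EASI the ratio is 0.99 to 1.01 throughout. A separately built simulation that added a sharp-threshold hazard gave attenuation of 1.9% to 6.6% at 15% events and 3.1% to 9.5% at 25%, with 99% to 100% of the slope recovered when pre-event EASI was used.

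**Variations.**
- Events unrelated to EASI: 1.00 with and without imputation.
- SD 9 assumed in the higher-severity stratum: 0.87–0.97 as planned, 1.00–1.02 imputed.
- Stronger correlation (AR(1) 0.85, or exchangeable 0.65): a loss of about 2% to 16% for event rates up to 25%.
- Equal response in all active arms (the section 14.1 planning assumption), slope fitted through placebo: 0.81–0.97 as planned, 0.95–1.00 imputed.
- Poor responders leaving mainly at high exposure: 1.06–1.16 as planned.
- Events driven by the EASI value that is lost (MNAR): 0.86–0.98 as planned, 0.90–0.99 imputed, so the remedy helps only in part.

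**At N=224.** With 15%/25% events, about 224 × 0.85 = 190 and 224 × 0.75 = 168 subjects contribute as planned, against about 218 and 212 with imputation.
- Mean ratio as planned: 0.984/0.978 (weak) and 0.959/0.943 (strong), a bias of 1.6% to 5.7%.
- Mean ratio imputed: 1.003/1.008 and 1.003/1.009, a bias under 1%.
- Slope SD, as a fraction of the true slope: 0.21–0.22 as planned, 0.21–0.23 imputed.
- Root mean square error, worst case: √(0.22² + 0.057²) = 0.227 as planned, √(0.23² + 0.009²) = 0.230 imputed. There is no practical difference.

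**The case against.** The best defence is the plan's own assumption. For the primary estimand, outcomes of subjects with events "are assumed to follow the outcome distribution for subjects in the same treatment group, who did not experience an intercurrent event". If that holds exactly, the Week 16 ANCOVA is unbiased, and the simulation agrees (1.00). A reader might infer from the contrast with the MMRM that the plan contradicts itself. It does not: the exposure-response model is valid under that assumption. It lacks the protection the MMRM also has when the assumption fails but missingness is still explained by observed interim EASI.

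Second, section 14.3.3 says the missing-data assumptions for section 14.3.8 will be elaborated in the SAP. No separate SAP is in the supplied text, so the omission is partly read from silence. This stands as a caution. But the sentence names no method for this analysis, and 14.3.8.4 itself defers only model fit and the non-linear form.

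Third, the gain is small: a bias of 2% to 6% beside a slope SD above 20%, with unchanged root mean square error, in an analysis that 14.3.7 calls exploratory. Dose identification also rests on the MMRM contrasts, which already use interim EASI. All of this stands and limits the priority.

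Fourth, a reader might infer that the slope must be flattened, or that the efficacy tests or Panel 17 power are affected. Neither is supported. Direction depends on who leaves and at what exposure, which the documents do not establish, and the gatekept tests use a different model.

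**Conclusion.** The point holds in conditional form and is worth a low-cost change. As written, the exposure-response slope is unbiased only if missingness is explained by trough, baseline EASI and region, or if the same-arm assumption is exactly true. If events also depend on interim EASI, expect a bias of typically 2% to 6% toward zero at assumed event rates of 15% to 25%, larger at higher rates or stronger correlation, and possibly away from zero if poor responders leave mainly at high exposure.

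These sizes are illustrative. Event rates, trajectories and doses are redacted, and the 0.65 correlation and 18.9 variance are stated only for the lower-severity stratum, planned at about 30% of subjects. Only a linear slope was tested. The benefit is removal of a small systematic error, not better precision.

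**What to change.** In section 14.3.8.4, or in the SAP that 14.3.1 says will be finalized before the randomization code is broken:

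- Multiply impute missing or excluded Week 16 EASI under MAR from baseline EASI, region, arm and/or exposure, and pre-event interim EASI. Follow the 14.3.8.2 procedure, but exclude data after any intercurrent event. Fit the exposure-response model to each dataset and pool.
- For subjects with no on-treatment Week 16 trough, use the last pre-event pre-dose sample from Weeks 4, 8 or 12 (Panel 3).
- Keep the imputation model compatible with the fitted model, for example by imputing within arm or using a flexible exposure term if Emax is fitted. The incomplete recovery in the equal-response setting (down to 0.95) is consistent with too rigid an exposure term.
- Keep the Week 16-only ANCOVA as a sensitivity analysis.

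The cost is SAP wording and modest programming, with no new samples or visits. Troughs would come from different visits, and section 9.2 requires the time of the last dose to be recorded only at Week 16 or the last visit, so the dosing interval before an earlier trough may be less well documented. Early leavers without any trough stay excluded: about 224 − 218 = 6 subjects at 15% events and 224 − 212 = 12 at 25%.

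Whether placebo enters at zero exposure, and how troughs taken during topical rescue or averaged troughs are used, are separate clarifications and not part of this point.
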